### 8.6.3 Adverse events requiring specific event forms in the eCRF

For some AEs the investigator must complete a specific event form in the eCRF in addition to the AE form. The AEs that require specific event forms are:

- Gallstone disease
- Neoplasms
- Pancreatitis

In case any of these events fulfil the criteria for a serious adverse event, please report accordingly (section [12.1](#)).

#### 8.6.3.1 Gallstone disease

If an event of acute gallstone disease or clinical suspicion of this is observed during the trial, this must be recorded as an AE and on a specific gallstone event form in the eCRF. The following information should be obtained, if available as part of standard of care:

- Signs and symptoms of acute gallstone disease

Protocol: Liraglutide  
Trial ID: NN8022-4179  
UTN: U1111-1162-7884  
EudraCT no.: 2014-004415-37

~~CONFIDENTIAL~~

Date: 16 July 2020  
Version: 5.0  
Status: Final  
Page: 61 of 125

**Novo Nordisk**

- Specific laboratory test supporting a diagnosis of gallstone disease:
  - White blood cell count (WBC)
  - C-reactive protein (CRP)
  - Direct, indirect and total bilirubin
  - ALT and AST
  - Alkaline Phosphatase (ALP)
  - Amylase
  - Lipase
- Imaging performed and consistency with gallstone disease
- Treatment given for the condition
- Relevant risk factors for gallstone disease including:
  - History of gallstones
  - Family history of gallstones
  - Relevant surgery

### **8.6.3.2 Neoplasms**

All events of benign, pre-malignant/carcinoma in-situ and malignant neoplasms must be reported during the trial. This must be recorded as an AE and on a specific neoplasm event form in the eCRF. The following information should be obtained if available as part of standard of care:

- Type of neoplasm
- Symptoms leading to identification of event
- Diagnostic imaging
- Pathological examination results
- Treatment for the event
- Participation in screening programs
- Risk factors associated to the event
- New diagnosis or recurrence/relapse of the neoplasm

### **8.6.3.3 Pancreatitis**

If an event of pancreatitis is observed during the trial, this must be recorded as an AE and on a specific pancreatitis event form in the eCRF. The following information should be obtained if available as part of standard of care:

- Signs and symptoms of pancreatitis
- Specific laboratory test supporting a diagnosis of pancreatitis:
  - Amylase
  - Lipase
  - ALT and AST
  - Bilirubin
  - Alkaline Phosphatase

Protocol: Liraglutide  
Trial ID: NN8022-4179  
UTN: U1111-1162-7884  
EudraCT no.: 2014-004415-37

~~CONFIDENTIAL~~

Date: 16 July 2020  
Version: 5.0  
Status: Final  
Page: 62 of 125

**Novo Nordisk**

- Imaging performed and consistency with pancreatic disease
- Treatment and complications to the event
- Relevant risk factors for pancreatic disease including:
  - History of gallstones
  - History of pancreatitis
  - Family history of pancreatitis
  - Trauma

## 8.7 Other assessments

### 8.7.1 Plasma concentration of liraglutide for pharmacokinetics

Blood samples for assessment of liraglutide plasma concentration are drawn from all subjects during the 16-week double-blind trial period as per section [2](#).

Subjects and subjects' LAR must be instructed to withhold their trial product dose in the morning until blood sampling is performed on the visit.

The subjects and subjects' LAR must be instructed to complete the dosing diary for liraglutide plasma concentration assessment (section [2](#)) and the dose, date and exact time for sampling the blood must be recorded in the eCRF.

The blood sample taken at V20 for liraglutide plasma concentration assessment from subjects treated with liraglutide only is not part of the pharmacokinetic/pharmacodynamic modelling plan (section [17.5](#)). The purpose of this assessment is to preclude any false negative antibody results. Hence recordings in the subject's dosing diary and eCRF are not requested for this sample.

Quality controlled data must be available for review by Development Bioanalysis prior to database lock (DBL).

### 8.7.2 Dietary and physical activity counselling

#### 8.7.2.1 Dietary counselling

Subjects and subjects' LAR must receive individualised dietary counselling with the goal of obtaining a weight loss. The counselling must be performed by a certified dietitian according to local standard. Individuals with Prader-Willi Syndrome have a different body composition with less muscle mass and a higher percentage of body fat even if they are at a normal body weight. As a result, their caloric needs are significantly lower and caloric intake should be restricted.

If a BMI corresponding to  $< 25 \text{ kg/m}^2$  for adults by international cut-off points is reached subjects should be assigned a maintenance diet.

Protocol: Liraglutide  
Trial ID: NN8022-4179  
UTN: U1111-1162-7884  
EudraCT no.: 2014-004415-37

~~CONFIDENTIAL~~

Date: 16 July 2020  
Version: 5.0  
Status: Final  
Page: 63 of 125

**Novo Nordisk**

Dietary counselling can be done in person or by phone/video conference according to the flowchart and must be documented in subject's medical record.

Dietary counselling should preferably take place within the visit window for the relevant visit.

Dietary compliance must be evaluated at every visit by the dietitian, using a numerical rating scale (NRS), and results must be provided to the investigator. The investigator or delegated staff must translate the NRS into a number and record the data into the eCRF.

#### **8.7.2.2 Counselling in physical activity**

At every site, there must be a qualified person (site staff trained in physical activity counselling) to provide instructions and advise on physical activity. An increase in physical activity is encouraged and reinforced at every visit.

#### **8.7.3 Subject diary**

Subjects will be provided with a paper diary to be completed at home. Only the subjects and/or the LAR must enter data in the diary. Subjects will be instructed by the investigator in when and how to complete the diary. It is important to explain to the subjects the necessity of accurate diary recording.

Review of diaries must be documented by the investigator, either on the documents and/or in the subject's medical record. If clarification of entries or discrepancies in the diary is needed, the subject must be questioned and a conclusion made in the subject's medical record. Care must be taken not to bias the subject and it is important to explain to the subjects the necessity of accurate diary recording.

All data from the diary must be transcribed into the eCRF.

The diary will include three different sections as specified in sections [8.7.3.1](#), [8.7.3.2](#) and [8.7.3.3](#)

##### **8.7.3.1 Dosing diary**

Dosing diary should be completed by the subject on the last three days before a visit including a blood sampling for liraglutide plasma concentration (section [8.7.1](#) and section [2](#)).

The last 3 doses of liraglutide must be recorded with:

- Dose

Protocol: Liraglutide  
Trial ID: NN8022-4179  
UTN: U1111-1162-7884  
EudraCT no.: 2014-004415-37

~~CONFIDENTIAL~~

Date: 16 July 2020  
Version: 5.0  
Status: Final  
Page: 64 of 125

**Novo Nordisk**

- Date
- Exact time

### **8.7.3.2 Hypoglycaemic episode diary**

The hypoglycaemic episode diary should be completed if the subject recognises a hypoglycaemic episode, i.e. a hypoglycaemic form for each episode (section [8.5.2](#))

### **8.7.3.3 Menstrual period diary**

The menstrual period diary forms should be completed by all female subjects of childbearing potential during the trial. The first day of all menstrual periods, if applicable, should be recorded in the diary.

## **8.8 Subject compliance**

To ensure subject trial compliance, the investigator and/or delegated staff should remind the subjects to follow the trial procedures and requirements throughout the trial. If a subject is found to be non-compliant, the investigator and/or delegated staff should remind the subject of the importance of following the instructions given including taking the trial products as prescribed.

Subject treatment compliance is assessed by monitoring of drug accountability. Prior to visits where drug accountability is performed, the subject should be asked to return all used, partly used and unused trial product. The investigator must assess the amount of trial product returned compared to what was dispensed at the last dispensing visit and, in case of discrepancies, question the subject (section [9.4](#))

Protocol: Liraglutide  
 Trial ID: NN8022-4179  
 UTN: U1111-1162-7884  
 EudraCT no.: 2014-004415-37

**CONFIDENTIAL**

Date: 16 July 2020  
 Version: 5.0  
 Status: Final  
 Page: 65 of 125

**Novo Nordisk**

## 9 Trial supplies

Trial supplies comprise trial products and auxiliary supplies. Additional details regarding trial supplies can be found in the Trial Materials Manual (TMM).

Trial products must not be dispensed to any person not included in the trial.

Liraglutide or liraglutide placebo must not be used, if it does not appear clear and colourless or almost colourless.

### 9.1 Trial products

The following trial products will be provided by Novo Nordisk A/S, Denmark:

**Table 9–1 Trial products**

Trial product Investigational medicinal product (IMP)	Strength	Dosage form	Route of administration	Delivery device
Liraglutide 6.0 mg/mL 3 mL cartridge	6.0 mg/mL	Solution for injection	Subcutaneous injection (s.c.)	3 mL FlexPen®
Liraglutide placebo 3 ml cartridge	N/A			

Liraglutide and liraglutide placebo are visually identical.

### 9.2 Labelling

The trial products will be labelled in accordance with Annex 13, local regulations and trial requirements.

Each trial site will be supplied with sufficient trial products for the trial on an on-going basis controlled by the IV/WRS. Dispensing unit numbers (DUNs) will be distributed to the trial sites according to enrolment and randomisation.

The investigator must document that direction for use is given to the subject orally and in writing at the first dispensing visit (V3). At all subsequent drug dispensing visits, directions for use should be handed out to subjects, if needed.

Protocol: Liraglutide  
 Trial ID: NN8022-4179  
 UTN: U1111-1162-7884  
 EudraCT no.: 2014-004415-37

**CONFIDENTIAL**

Date: 16 July 2020  
 Version: 5.0  
 Status: Final  
 Page: 66 of 125

**Novo Nordisk**

### 9.3 Storage

**Table 9–2 Storage**

Trial product	Storage conditions (not-in-use)	In-use conditions	In-use time*
Liraglutide 6.0mg/mL	Store in a refrigerator between 2°C to 8°C (36°F to 46°F) Protect from light Do not freeze	At temperatures below 30°C or in a refrigerator between 2°C to 8°C US: At room temperature (59°F to 86°F) or in a refrigerator (36°F to 46°F) Protect from light Do not freeze	Use within one month US: Use within 30 days
Liraglutide placebo			

\* In-use time starts when first dose is taken or used as spare pen.

The investigator must ensure the availability of proper storage conditions, and also record and evaluate the temperature. The investigator must inform Novo Nordisk **immediately** if any trial product has been stored outside specified conditions (e.g. outside temperature range).

Trial product that has been stored improperly must not be dispensed to any subject before it has been evaluated and approved for further use by Novo Nordisk. The investigator must take appropriate action to ensure correct storage.

### 9.4 Drug accountability and destruction

Drug accountability is the responsibility of the investigator.

Subjects must be instructed to return all used, partly used and unused trial products including empty packaging material at each dispensing visit.

Returned trial product (used/partly used or unused including empty packaging material) can be stored at room temperature and must be stored separately from non-allocated trial product.

Drug accountability is performed by using the IV/WRS drug accountability module. Only dispensed DUNs (= Dispensing Unit Numbers) returned by the subject (used/partly used or unused) are accounted for.

Destruction will be done according to local procedures after accountability is finalised and verified by the monitor. Destruction of products must be documented.

Protocol: Liraglutide  
Trial ID: NN8022-4179  
UTN: U1111-1162-7884  
EudraCT no.: 2014-004415-37

~~CONFIDENTIAL~~

Date:  
Version:  
Status:  
Page:

16 July 2020  
5.0  
Final  
67 of 125

**Novo Nordisk**

## 9.5 Auxiliary supplies

The following will be provided by Novo Nordisk in accordance with the TMM:

- Direction for Use for the FlexPen®
- Needles for the device with a maximum needle length of 8 mm
- Blood glucose meters (BG meters) and BG-meter auxiliaries

Protocol: Liraglutide  
Trial ID: NN8022-4179  
UTN: U1111-1162-7884  
EudraCT no.: 2014-004415-37

~~CONFIDENTIAL~~

Date: 16 July 2020  
Version: 5.0  
Status: Final  
Page: 68 of 125

**Novo Nordisk**

## 10 Interactive voice/web response system

A trial-specific IV/WRS will be set up which can be accessed at any time via the internet or telephone. Access to the IV/WRS must be restricted to and controlled by authorised persons.

IV/WRS is used for:

- Screening
- Screening failure
- Randomisation
- Medication arrival
- Dispensing
- Treatment discontinuation
- Completion
- Code break
- Drug accountability
- Data change

IV/WRS user manuals will be provided to each trial site.

DUNs will be allocated using IV/WRS. It is important to dispense the exact allocated DUNs to a subject. The subject's treatment allocation will be revealed using the IV/WRS at V10.

Protocol: Liraglutide  
Trial ID: NN8022-4179  
UTN: U1111-1162-7884  
EudraCT no.: 2014-004415-37

CONFIDENTIAL

Date: 16 July 2020  
Version: 5.0  
Status: Final  
Page: 69 of 125

Novo Nordisk

## 11 Randomisation procedure and breaking of blinded codes

Randomisation will be stratified according to pubertal status and by presence/absence of dysglycaemia. Stratification will be controlled by the IV/WRS. The stratification factors are:

Pubertal status:

- Tanner below 2 (defined as Tanner stage 1 with or without premature adrenarche) (part B only)
- Tanner 2 or 3 (part A only)
- Tanner 4 or 5 (part A only)

Glycaemic status:

- dysglycaemia yes
- dysglycaemia no

Dysglycaemia is defined as pre-diabetes with FPG 5.6 – 6.9 mmol/L (both inclusive) (100 - 125 mg/dL) (both inclusive) and/or HbA1c 5.7 – 6.4 % (both inclusive). The HbA1c and FPG results from V2 must be used.

At randomisation, the subjects will be randomised to one of two parallel treatment groups: liraglutide or placebo. The randomisation will be carried out in a 2:1 manner using the IV/WRS.

The trial is a double-blind trial for the first 16 weeks followed by a 36 weeks open-label treatment period. Only subjects treated with liraglutide will receive trial treatment in the 36-weeks open-label treatment period. The subject's treatment allocation will be un-blinded on an on-going basis after the double blind period at week 16 (V10).

### 11.1 Breaking of blinded codes

The IV/WRS will notify Novo Nordisk (monitor and the Global Safety department) immediately after the code is broken.

The code for a particular subject may be broken in a medical emergency if knowing the actual treatment would influence the treatment of the subject. Whenever a code is broken the person breaking the code must print the Code Break Confirmation Notification generated by the IV/WRS, record the reason, and sign and date the document.

When the code is broken, the treatment allocation will be accessible to the investigator and the Novo Nordisk Global Safety department. If IV/WRS is not accessible at the time of code break the IV/WRS helpdesk should be contacted. Contact details are listed in [Attachment I](#).

If the code has been broken the subject is allowed to continue in the trial. If the subject must be withdrawn from the trial, a withdrawal session must be completed in IV/WRS.

Protocol: Liraglutide  
Trial ID: NN8022-4179  
UTN: U1111-1162-7884  
EudraCT no.: 2014-004415-37

~~CONFIDENTIAL~~

Date:	16 July 2020	Novo Nordisk
Version:	5.0	
Status:	Final	
Page:	70 of 125	

## 11.2 Laboratory access to blinded data

The special laboratories analysing the samples for anti-liraglutide antibodies and concentration of liraglutide will be provided with a randomisation list. This procedure will be described in a blinding plan.

Protocol: Liraglutide  
 Trial ID: NN8022-4179  
 UTN: U1111-1162-7884  
 EudraCT no.: 2014-004415-37

~~CONFIDENTIAL~~

Date: 16 July 2020  
 Version: 5.0  
 Status: Final  
 Page: 71 of 125

**Novo Nordisk**

## 12 Adverse events, technical complaints and pregnancies

### 12.1 Definitions

#### Adverse event

An adverse event (AE) is any untoward medical occurrence in a subject administered a product, and which does not necessarily have a causal relationship with this treatment.

An AE can therefore be any unfavourable and unintended sign (including an abnormal laboratory finding), symptom or disease temporally associated with the use of a product, whether or not considered related to the product.

An AE includes:

- A clinically significant worsening of a concomitant illness.
- A clinical laboratory adverse event (CLAE): a clinical laboratory abnormality which is clinically significant, i.e. an abnormality that suggests a disease and/or organ toxicity and is of a severity that requires active management. Active management includes active treatment or further investigations, for example change of medicine dose or more frequent follow-up due to the abnormality.

The following should **not** be reported as AEs:

- Pre-existing conditions, including those found as a result of screening procedures (pre-existing conditions should be reported as medical history or concomitant illness).
- Pre-planned procedures unless the condition for which the procedure was planned has worsened from the first trial related activity after the subject has signed the informed consent.

The following three definitions are used when assessing an AE:

- **Severity**
  - **Mild** - no or transient symptoms, no interference with the subject's daily activities.
  - **Moderate** - marked symptoms, moderate interference with the subject's daily activities.
  - **Severe** - considerable interference with the subject's daily activities; unacceptable.
- **Causality**  
 Relationship between an AE and the relevant trial product(s):
  - **Probable** - Good reason and sufficient documentation to assume a causal relationship.
  - **Possible** - A causal relationship is conceivable and cannot be dismissed.
  - **Unlikely** - The event is most likely related to aetiology other than the trial product.

Protocol: Liraglutide  
Trial ID: NN8022-4179  
UTN: U1111-1162-7884  
EudraCT no.: 2014-004415-37

CONFIDENTIAL

Date: 16 July 2020  
Version: 5.0  
Status: Final  
Page: 72 of 125

Novo Nordisk

- **Final outcome**

- **Recovered/resolved** - The subject has fully recovered, or by medical or surgical treatment the condition has returned to the level observed at the first trial-related activity after the subject signed the informed consent.
- **Recovering/resolving** - The condition is improving and the subject is expected to recover from the event. This term is only applicable if the subject has completed the trial or has died from another AE.
- **Recovered/resolved with sequelae** - The subject has recovered from the condition, but with lasting effect due to a disease, injury, treatment or procedure. If a sequela meets an SAE criterion, the AE must be reported as an SAE.
- **Not recovered/not resolved** - The condition of the subject has not improved and the symptoms are unchanged, or the outcome is not known.
- **Fatal** - This term is only applicable if the subject died from a condition related to the reported AE. Outcomes of other reported AEs in a subject before he/she died should be assessed as "recovered/resolved", "recovering/resolving", "recovered/resolved with sequelae" or "not recovered/not resolved". An AE with fatal outcome must be reported as an SAE.
- **Unknown** - This term is only applicable if the subject is lost to follow-up.

**Serious adverse event**

A serious adverse event (SAE) is an experience that at any dose results in any of the following:

- Death.
- A life-threateninga experience.
- In-patient hospitalisationb or prolongation of existing hospitalisation.
- A persistent or significant disability or incapacityc.
- A congenital anomaly or birth defect.
- Important medical events that may not result in death, be life threateninga or require hospitalisationb may be considered an SAE when - based on appropriate medical judgement - they may jeopardise the subject and may require medical or surgical intervention to prevent one of the outcomes listed in the definition of SAEd.

a. The term "life threatening" in the definition of SAE refers to an event in which the subject was at risk of death at the time of the event. It does not refer to an event which hypothetically might have caused death if it was more severe.

b. The term "hospitalisation" is used when a subject:

- Is admitted to a hospital or in-patient, irrespective of the duration of physical stay, or
- Stays at the hospital for treatment or observation for more than 24 hours

Protocol: Liraglutide  
Trial ID: NN8022-4179  
UTN: U1111-1162-7884  
EudraCT no.: 2014-004415-37

~~CONFIDENTIAL~~

Date: 16 July 2020  
Version: 5.0  
Status: Final  
Page: 73 of 125

**Novo Nordisk**

Medical judgement must always be exercised, and when in doubt, the hospital contact should be regarded as a hospitalisation. Hospitalisations for administrative, trial related and social purposes do not constitute AEs and should therefore not be reported as AEs or SAEs. Hospital admissions for surgical procedures, planned before trial inclusion, are not considered AEs or SAEs.

- c. A substantial disruption of a subject's ability to conduct normal life functions (e.g. following the event or clinical investigation the subject has significant, persistent or permanent change, impairment, damage or disruption in his/her body function or structure, physical activity and/or quality of life).
- d. For example intensive treatment in an emergency room or at home of allergic bronchospasm, blood dyscrasias or convulsions that do not result in hospitalisation, or development of drug dependency or drug abuse.

The following AEs must always be reported as an SAE using the important medical event criterion if no other seriousness criteria are applicable:

- suspicion of transmission of infectious agents via the trial product
- risk of liver injury defined as alanine aminotransferase (ALT) or aspartate aminotransferase (AST) >3 x ULN and total bilirubin >2 x ULN, where no alternative aetiology exists (Hy's law).

### **Non-serious adverse event**

A non-serious AE is any AE which does not fulfil the definition of an SAE.

### **Medical event of special interest**

A medical event of special interest (MESI) is an event which, in the evaluation of safety, has a special focus. A MESI is an AE (SAE or non-serious AE) which fulfils one or more of the below defined MESI criteria.

1. Medication errors concerning trial products:
  - Administration of wrong drug or use of wrong device.
  - Note: Use of wrong DUN is not considered a medication error.
  - Wrong route of administration, such as intramuscular instead of subcutaneous.
  - Administration of an overdose with the intention to cause harm (e.g. suicide attempt).
  - Accidental administration of a lower or higher dose than intended. These are doses lower or higher than 0.6, 1.2, 1.8, 2.4 and 3.0 mg respectively for subjects in part A and part B (children with a body weight  $\geq$  45 kg) and doses lower than 0.3, 0.6, 1.2, 1.8 and 2.4 mg respectively for subjects in part B (children with a body weight < 45 kg) (within 24 hours). However the administered dose must deviate from the intended dose to an extent where

Protocol: Liraglutide  
Trial ID: NN8022-4179  
UTN: U1111-1162-7884  
EudraCT no.: 2014-004415-37

CONFIDENTIAL

Date: 16 July 2020  
Version: 5.0  
Status: Final  
Page: 74 of 125

Novo Nordisk

clinical consequences for the trial subject were likely to happen as judged by the investigator, although they did not necessarily occur.

When reporting a MESI, the following forms must be completed: the AE form, SIF and specific MESI form, as described in section [12.2](#) and illustrated in [Figure 12-1](#).

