**Novo Nordisk**

### 5.3 Treatment of subjects

Liraglutide or liraglutide placebo will be administered by once-daily subcutaneous (s.c.) injections either in the abdomen, thigh, or upper arm; injection site consistency is not required throughout the trial. During the 16-week double-blind period, subjects randomised to receive liraglutide placebo will receive placebo s.c. injections with injection volumes equivalent to the corresponding liraglutide dose. Liraglutide placebo contains the same excipients as liraglutide, but no active trial product. Injections can be administered at any time of day irrespective of meals. It is recommended that the time of injection is consistent throughout the trial. Subjects will be instructed to perform an air shot before the use of a new pre-filled pen. At the end-of the double-blind period, subjects randomised to receive placebo will stop injections once the investigator and subject are un-blinded to treatment allocation. During the 36-week open-label period, subjects in the liraglutide group will continue to receive liraglutide treatment. The maximum duration of treatment of a single subject, from first trial product administration to last trial product administration will be 52 weeks, and the maximum dose will be 3.0 mg/day in part A and for children in part B with a body weight  $\geq 45$  kg. For children in part B with a body weight of  $< 45$  kg the maximum dose will be 2.4 mg/day.

At the first visit subjects and their LAR will be instructed in symptoms and treatment of hypoglycaemia, and in blood glucose measurements. The liraglutide dose will not be escalated if the subject experiences SMBG  $< 3.1$  mmol/L (56 mg/dL) or  $< 3.9$  mmol/L (70 mg/dL) in the presence of symptoms of hypoglycaemia, during the week prior to the dose escalation visit.

The following medications should not be used: orlistat, zonisamide, topiramate/phentermine, lorcaserin, phentermine and bupropion/naltrexone. Except for liraglutide as trial medication, GLP-1 receptor agonists cannot be prescribed during the trial. Metformin can only be used if the subject develops T2DM requiring an anti-diabetic agent as described in section [5.3.3](#).

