#### 5.3.1.2 Dose escalation part B

Based on result of the safety and PK data of NN8022-4181 and part A of NN8022-4179, the recommendation for part B - PWS children (aged 6 to < 12 years) with obesity is to initiate treatment with liraglutide/placebo based on weight.

Protocol: Liraglutide  
Trial ID: NN8022-4179  
UTN: U1111-1162-7884  
EudraCT no.: 2014-004415-37

CONFIDENTIAL

Date: 16 July 2020  
Version: 5.0  
Status: Final  
Page: 33 of 125

Novo Nordisk

For children with a body weight  $\geq 45$  kg, dosing will be initiated with liraglutide/placebo 0.6 mg daily for one week and increased in weekly steps of 0.6 mg until a maximum tolerated dose (MTD) (as judged by the investigator) or a dose of 3.0 mg liraglutide/placebo is reached.

For children with a body weight  $< 45$  kg, dosing will be initiated with liraglutide/placebo 0.3 mg daily for one week and increased to 0.6 mg after the first week, thereafter the dose is increased in weekly steps of 0.6 mg until a MTD (as judged by the investigator) or a dose of 2.4 mg liraglutide/placebo is reached.

Escalation of the liraglutide/placebo dose is not allowed if the subject has a SMBG  $< 3.1$  mmol/L (56 mg/dL) or  $< 3.9$  mmol/L (70 mg/dL) in the presence of symptoms of hypoglycaemia during the week prior to the dose escalation visits.

Hypoglycaemic episodes must be reported according to Section [8.5.2](#).

Dose escalation will be based on tolerability as assessed by the investigator. The trial product dose will be escalated only if the current dose is tolerated. If a subject has tolerability issues with the higher dose level (as judged by the investigator), it is allowed to lower to the previous dose level.

If a trial product dose is poorly tolerated during the dose escalation period, subjects are allowed to remain at a dose level for an additional week, i.e. four times in total, thus the dose escalation will last for eight weeks in total as a maximum.

Visits and phone contacts to the clinic occur weekly during dose escalation.

Trial Product dose at V8 will be defined as MTD.

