**Novo Nordisk**

the start of treatment the 0.3 mg starting dose with a cap of 2.4 mg/day as a maximum dose for subjects < 45 kg is introduced.

The treatment duration of 16 weeks is considered adequate for evaluation of the effect of liraglutide on the primary efficacy endpoint during the double-blind period. The 36-week open-label period will provide supportive information on the effect of liraglutide on other efficacy endpoints and establish the safety profile of liraglutide in this patient population. A placebo group is included in the trial to compare safety between placebo and liraglutide treatment. The s.c. injection is the route of administration intended for clinical use of liraglutide.

For more information, see the latest edition of the Investigator's Brochure for: Liraglutide (NN8022) in Weight Management or any updates hereof.

Protocol: Liraglutide  
Trial ID: NN8022-4179  
UTN: U1111-1162-7884  
EudraCT no.: 2014-004415-37

~~CONFIDENTIAL~~

Date:  
Version:  
Status:  
Page:

16 July 2020  
5.0  
Final  
36 of 125

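### The medication-error MESI criterion in protocol section 12.1 omits *or higher* for part B children below 45 kg, contradicting its own opening sentence and leaving the reporting of accidental higher doses in that group ambiguous

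*Protocol*

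**What the plan says.** In protocol section 12.1, under the MESI definition, medication errors are the listed criterion. The bullet on accidental dosing has three parts.

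- **Opening sentence:** "Accidental administration of a lower or higher dose than intended". It names no weight group.
- **Specifying sentence:** for part A and the heavier part B children, "These are doses lower or higher than 0.6, 1.2, 1.8, 2.4 and 3.0 mg respectively for subjects in part A and part B" (45 kg or more). For the lighter part B children, "and doses lower than 0.3, 0.6, 1.2, 1.8 and 2.4 mg respectively for subjects in part B" (below 45 kg).
- **Qualifier:** "However the administered dose must deviate from the intended dose to an extent where" clinical consequences were likely in the investigator's judgement, whether or not they followed. It names neither a direction nor a weight group.

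The dosing sections treat the lighter children separately. In section 5.3.1.2, for those below 45 kg, "dosing will be initiated with liraglutide/placebo 0.3 mg daily for one week and increased to 0.6 mg after the first week". Section 5.5 describes "the 0.3 mg starting dose with a cap of 2.4 mg/day as a maximum dose for subjects" below 45 kg as a precaution, and gives the limited data in patients of that weight as the reason for the weight-based scheme.

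**The concern.** The specifying sentence is worded as the explanation of the opening one. For the lighter children it covers one direction where the opening sentence covers two, and it gives no reason. A site reading the bullet cannot tell which sentence governs an accidental higher dose in a child below 45 kg.

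This is an operative rule, because MESI status changes what is sent and when (sections 12.2 and 12.3). A site that relied on the clause for lighter children could treat a non-serious accidental overdose as an ordinary adverse event. It would then send no safety information form and no MESI form, and would follow no 14-day timeline. The missing direction also matters in practice. Part B runs two dose schedules side by side, so a lighter child given a dose from the heavier children's schedule is a foreseeable error, and it can be an error upwards.

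**Working it through.** The point depends on no sample size, error rate or effect size, so the check is a comparison of texts.

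**1. Direction of deviation covered, by sentence of the bullet**

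| Part of the bullet | Part A, and part B 45 kg or more | Part B below 45 kg |
|---|---|---|
| Opening sentence | lower and higher | lower and higher |
| Specifying sentence | lower and higher, at 5 dose levels | lower only, at 5 dose levels |
| Qualifier | no direction named | no direction named |

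For the heavier group the sentences agree. For the lighter group, the specifying sentence lists a higher-than-intended dose at 0 of 5 levels, while the opening sentence includes it at all of them.

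**2. Are the listed dose levels themselves right?** Yes. The levels 0.3, 0.6, 1.2, 1.8 and 2.4 mg match the escalation in section 5.3.1.2, the reductions in section 5.3.2, and section 5.3, where for part B children of less than 45 "kg the maximum dose will be 2.4 mg/day". The fault is confined to the direction.

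**3. Illustration.** In week 1 the intended dose is 0.3 mg for a child below 45 kg and 0.6 mg for a heavier child (section 5.3.1.2). Suppose a lighter child is given 0.6 mg by mistake, which is 0.6 / 0.3 = 2 times the intended dose. Under the opening sentence this is in scope, subject to the qualifier. Under the specifying sentence it is not listed. The same holds at the top of the schedules: 3.0 mg instead of 2.4 mg is 3.0 / 2.4 = 1.25 times the intended dose. Whether either case would meet the investigator-judged threshold is not something the documents settle.

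**4. Does another passage resolve it?**
- The other overdose bullet in section 12.1 covers only overdose intended to cause harm.
- Section 12.6 reports experience with overdose and sets no reporting rule.
- Sections 12.2 and 12.3 use the MESI category but do not restate the criterion.
- The SAP does not define MESIs.
- Figure 12-1 is not shown in the available text and could not be checked.

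**5. What MESI status adds**

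| Event | Required regardless of MESI status | Added by MESI status |
|---|---|---|
| Serious | AE form within 24 hours, safety information form within 5 calendar days | MESI form within 14 calendar days |
| Non-serious | AE form, signed at resolution or at trial end | Safety information form and MESI form, with all three forms due within 14 calendar days; follow-up information within 14 calendar days |

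For a non-serious event that is not a MESI and needs no additional data collection, section 12.2 sets no initial deadline. Section 13.2 only states a preference for entry within 5 days after the visit.

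**6. How many subjects.** Section 6.1 plans 24 subjects in part B, and Table 17-2 splits them 16 + 8 = 24 between liraglutide and placebo. The share below 45 kg is not given, so the affected group lies between 0 and 24. At most 16 could receive an excess of active drug. Sites are blinded for the first 16 weeks, so during that period the reporting question arises in either arm.

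**The case against.** A reader might infer that accidental overdoses in the lightest children are excluded from the MESI definition. The documents do not support that. The opening sentence includes higher doses for every subject, and the qualifier speaks only of deviation from the intended dose. One clause is silent where the rest of the bullet is not, which makes the rule contradictory but does not exclude these cases. Nor do the documents show a decision to treat overdose differently in lighter children. The precaution described in section 5.5 points the other way, and a drafting omission is the most plausible explanation.

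The consequence is also bounded. Every event that meets the AE definition must be reported under section 12.2, and serious events keep their 24-hour and 5-day deadlines. No endpoint rests on MESI status, and the SAP's adverse event summaries do not use it.

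All of this stands, and it limits the point to an ambiguity in safety reporting. It does not remove it. General AE reporting is an incomplete backstop, because the MESI criterion also reaches errors whose consequences were likely but did not occur. An accidental higher dose without symptoms is not clearly an adverse event under the general definition in section 12.1, so the MESI bullet is the plainest route by which it would be captured.

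**Conclusion.** Wrong as written, as an internal inconsistency and not as a design choice. For part B children below 45 kg, the opening and specifying sentences of one bullet disagree on whether an accidental higher-than-intended dose counts as a MESI, and nothing else in the protocol or SAP settles it.

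The size is modest. It concerns at most the 24 children planned for part B, fewer if some weigh 45 kg or more, and only errors that meet the investigator-judged threshold. The documents give no expected number of such errors. What could be lost is the MESI form for a serious event, and for a non-serious one also the safety information form and the 14-day timelines. It still merits correction, because it affects reporting in the group for which the protocol itself cites limited data. The conclusion assumes that Figure 12-1 does not restate the criterion differently.

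**What to change.** The sponsor should reconcile the two sentences in protocol section 12.1 so that the direction of deviation counted as a MESI is consistent for part B children below 45 kg. If a difference between the weight groups is intended, the protocol should state it and give the reason. Sites should be told which reading applies, and Figure 12-1 and the instructions for the MESI form should be checked for the same wording. It would be sensible to ask sites whether any higher-than-intended dose in this group has already been handled without a MESI form.

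The cost is a few words in section 12.1 and a note to sites. No dose, clinical rule, endpoint or analysis changes.
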